# 6.3.2.3. Power Calculations for Evaluation of Efficacy

This trial is designed as an event driven study to test the null hypothesis that VE  $\leq 20\%$ . The efficacy endpoint will be evaluated once a fixed number of ZIKV cases have occurred. Table 9 provides the number of cases that are required to achieve 80% and 90% power for the test of the null hypothesis (VE  $\leq 20\%$ ) for various assumed VEs using the R function binom.power. For this calculation, we note that conditional on the total number of cases, the probability a case comes from the vaccine group is equal to (1-VE)/(2-VE). Thus, the null probability that a case comes from the vaccine is given by (1-0.2)/(2-0.2) = 4/9. Simulations show that power from this conditional binomial calculation is an excellent approximation to the power from a Cox regression model which will be used for analysis. With ninety cases of virologic ZIKV infection, the study is capable of detecting a vaccine efficacy of 61% with 90% power. While these calculations assume there is no interim monitoring and the study will be monitored using an O'Brien-Fleming boundary for efficacy, such monitoring has a negligible impact on power.

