# 6.4.4. Analysis of ZIKV Incidence

Efficacy evaluation with respect to ZIKV incidence will be performed in **Part B**. Incidence rates for ZIKV cases will be described by vaccine group and by baseline ZIKV stratum for each group. Results will be treated both as dichotomous (infection, no infection) and as a time to event (infection) variables. The primary analysis will be based on the time to case of virologic ZIKV infection, i.e., when a subject is positive for ZIKV based on a PCR test. The time to ZIKV case data, accounting for censoring, will be described using Kaplan-Meier curves and efficacy computed using a Cox proportional hazards model. VE will be estimated by the hazard ratio from the Cox proportional hazards model stratified by baseline ZIKV exposure status.

The primary efficacy analysis is a test of the null hypothesis (H0): the study vaccine has VE no more than 20% in preventing ZIKV infection, i.e., VE  $\leq$  20%, where ZIKV infection is defined as virologically confirmed infection by PCR virus detection. The alternative hypothesis is that VE > 20%. The criterion for success will be that a one-sided test of H0 has p-value  $\leq$  0.025. This primary analysis will be based on the mITT cohort stratified by baseline serostatus (prior exposed to ZIKV or not). If the null VE  $\leq$  20% is not rejected, an additional test of H0\*: VE = 0 will be conducted using a one-sided type I error rate of 0.025.

The secondary efficacy analyses include the testing of this hypothesis over the two stratum combined. Another secondary analysis will test the above hypothesis H0, where ZIKV infection is defined as PCR virus detection irrespective of symptoms. The SAP will provide any necessary additional specificity and/or cohort definitions such as discussed at the beginning of Section 6.4.

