#### Efficacy Reviews (Part B only):

The final efficacy analysis will occur when the total number of virologic ZIKV cases in **Part B** of the study reaches 90. Interim efficacy analysis will be performed when the total number of virologic ZIKV cases in the mITT cohort reaches 30 and 60. To preserve a one-sided type I error rate of 2.5%, the Lan-DeMets spending function will be adopted. The Lan-DeMets analog of the O'Brien-Fleming boundary, or equivalently, the nominal significance of 0.0001, 0.006, and 0.023 will be used in the two interim analyses and the final analysis, respectively, for declaring efficacy. These tests will be of the null H0: VE  $\leq 20\%$ .

To examine for harm (i.e., a greater rate of ZIKV cases in the vaccine arm) a 95% nominal CI for the hazard ratio will be calculated. A guideline for stopping is met if this CI excludes 0 in the direction of harm. Harm will be monitored after 15, 30, 45, 60, and 75 cases have accrued. Harm will be monitored using both the ITT and mITT cohorts.

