## 2.1. Purpose of the Analyses

Note, not all analyses for endpoints included in the protocol are detailed in this plan. The exploratory endpoint analyses are not included in this SAP.

In **Part A**, the primary objective is to evaluate the safety and tolerability of the vaccine. In **Part B**, the primary objectives are to evaluate the safety and efficacy of the vaccine compared to the placebo. Secondary and exploratory objectives of the study relate to immunogenicity and durability of immune responses.

The VRC 705 protocol calls for multiple planned interim analyses. During **Part A** of the study immunogenicity may be analyzed in an ongoing fashion. During **Part B** of the study the following interim analyses will be performed:

- 1. Interim immunogenicity analyses may be performed after the neutralizing antibody (NAb) assays up to and including Week 12 have been completed on a subset of subjects.
- 2. Interim efficacy analysis may be performed when the total number of ZIKV cases in the modified Intent-to-treat (mITT) cohort reaches 30 and 60.

For **Part B**, the final efficacy analysis will occur when the total number of virologic ZIKV cases in the mITT cohort reaches 90 or study completion. The final analysis of **Part A** and **Part B** will be performed and completed when all primary and secondary safety, efficacy, and immunogenicity endpoint data are available, and the study database has been locked. The study clinical database and immunogenicity/efficacy database will be locked separately; the final analysis of **Part A** and **Part B** safety data will follow the clinical database lock and the final analysis of **Part A** and **Part B** immunogenicity and efficacy data will follow the second database lock once all lab data are received and validated.

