### 6.2. Timing of Analyses

- 1. Interim immunogenicity analyses for **Part A** may be performed on an ongoing basis, per sponsor directive.
  - a) The first interim immunogenicity analysis will be performed when 10 subjects in each group have data available through Visit 05
- 2. Interim immunogenicity analyses for **Part B** may be performed on a subset of subjects after the NAb assays up to and including Week 12 have been completed for the subset of subjects.
- 3. Final Efficacy Analysis will occur when the total number of mITT virologic ZIKV cases (primary efficacy endpoint) in **Part B** of the study reaches 90 or study completion.
- 4. The Final Analysis of safety data for both Part A and Part B will be performed after clinical database lock when all subjects have been followed through 32 weeks after the last product administration for Part A and at least 6 months after the first product administration for Part B. Final analysis of the efficacy and immunogenicity endpoint data will follow the database lock of the immunogenicity and efficacy data once all lab data are received and validated.
- 5. Exploratory Immunogenicity Analyses may be completed following database lock as assay results become available.

For all analyses completed prior to database lock, individual subjects' study group assignments will not be unblinded with the possible exception of a review of selected AEs or episodes of ZIKV disease for safety monitoring requirements, as described in the Study Blinding Plan.

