#### 6.6.3. Incidence Reviews (Part B only):

The study will be regularly monitored using the combined (blinded) incidence rates for ZIKV disease and for ZIKV infections. These rates will be monitored at each site and over all sites combined. Such monitoring will allow for enrollment to be expanded or curtailed at different sites.

Prior to completion of enrollment of the 2400 Part B subjects, calculations using the blinded incidence rates will be performed to estimate the expected time to achieve 90 cases of ZIKV disease. Based on these calculations, the sample size may remain fixed at 2400, be increased up to 15,000, or the trial may be stopped for lack of feasibility if this expected time is deemed excessive.

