#### **10.2.** Analysis of vaccine efficacy:

The time of ZIKV events is defined as the illness onset date recorded on the ZIKV Endpoints eCRF (for clinical cases) or date first specimen was collected with a positive PCR or other Zika result, whichever is earliest. Time to event for analysis will be as follows:

- For subjects with infection: time of ZIKV event minus date of first administration (Visit 02) + 1.
- For subjects with no infection: date of protocol completion/termination as recorded on the study status eCRF minus date of first administration (Visit 02) + 1. These subjects will be censored at their date of study completion or date of early termination.
- Subjects with or without infection may be censored from the analysis for the PP population as described in Section 6.3.

For subjects who were randomized but did not receive any product, date of randomization will be used in place of date of first administration in the definitions above.

The cumulative incidence of ZIKV cases will be presented graphically as 1 – Kaplan-Meier curves. Curves will be presented by study group and baseline ZIKV stratum and by study group combined over all subjects (Figure 27 through Figure 44, Appendix 2). Similar presentations will be displayed for virologic ZIKV cases and subclinical ZIKV cases).

Vaccine efficacy will be estimated as 1 - Hazard Ratio estimated from a Cox proportional hazard model. The primary efficacy analysis for ZIKV infection will use the following test:

H0: VE 
$$\leq 20\%$$
  
H1: VE  $\geq 20\%$ 

The criterion for success will be that a one-sided test of  $H_0$  has p-value  $\leq 0.025$ . Success will be met if the lower bound of the 95.0% confidence interval for VE estimated for the mITT population using a Cox proportional hazards model stratified by baseline ZIKV status is >20 (Table 51 through Table 53, Appendix 1).

If the null hypothesis VE  $\leq 20\%$  is not rejected, then the following will be tested using a one-sided type I error rate of 0.025.

H\*0: VE =0% H\*1: VE >0%

As secondary analyses of vaccine efficacy this hypothesis will be tested for:

- ZIKV cases without stratification for baseline ZIKV serostatus
- virologic ZIKV cases stratified by baseline ZIKV serostatus
- subclinical ZIKV cases stratified by baseline ZIKV serostatus
- subclinical ZIKV cases without stratification for baseline ZIKV serostatus

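### SAP 10.2 decides the primary efficacy test at one-sided 0.025 (95.0% CI), but Protocol 6.4.5 leaves 0.023 for the final analysis after looks at 30 and 60 cases

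*Combined protocol and SAP*

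**What the plan says.** **Protocol.** Section 6.4.5 (Efficacy Reviews) commits to interim efficacy analyses at 30 and 60 mITT cases and a final analysis at 90. It states the aim: "To preserve a one-sided type I error rate of 2.5%, the Lan-DeMets spending function will be adopted". It then fixes the levels: "the nominal significance of 0.0001, 0.006, and 0.023 will be used in the two interim analyses and the final analysis", all for H0: VE ≤ 20%. Section 6.3.2.3 also says the study will be monitored with an O'Brien-Fleming efficacy boundary. Section 6.4.4 sets the primary criterion ("The criterion for success will be that a one-sided test of H0 has p-value" at or below 0.025) without saying whether 0.025 is the overall level or the level of the final look.

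**SAP.** Section 10.2 repeats the 0.025 criterion for the same H0 and turns it into an interval rule: "Success will be met if the lower bound of the 95.0% confidence interval for VE estimated for the mITT population", from a Cox model stratified by baseline ZIKV status, exceeds 20. The sample code in 10.2.1 produces the default 95% interval. On the looks, SAP 2.1 is mixed. The sentence introducing the list says the interim analyses will be done, but the efficacy item says the analysis "may be performed when the total number of ZIKV cases in the modified Intent-to-treat (mITT) cohort reaches 30 and 60". SAP 6.6 covers safety reviews, immunogenicity reviews and blinded incidence reviews ("calculations using the blinded incidence rates will be performed to estimate the expected time to achieve 90 cases of ZIKV disease"). It has no efficacy review, and no boundary or spending function appears in the SAP. SAP 6.2 allows the final efficacy analysis when the mITT case count in Part B "of the study reaches 90 or study completion".

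**The concern.** Both documents state a final success rule for the same null hypothesis in the same population, at different thresholds. A final p-value between 0.023 and 0.025 is a success under SAP 10.2 and a failure under Protocol 6.4.5. If alpha has been spent at earlier looks, an unadjusted 95.0% interval at the end spends part of it twice, and the 2.5% that the protocol sets out to preserve is exceeded. Because the final analysis may fall at study completion with a count other than 90, a fixed 0.023 would not always be the right level either.

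**Working it through.** **Inputs.** Overall one-sided level 0.025, nominal levels 0.0001, 0.006, 0.023, and 30, 60 and 90 cases (Protocol 6.4.5), so information fractions t = 1/3, 2/3, 1. Null hazard ratio 0.80, conditional null probability 4/9, design VE 61% (Protocol 6.3.2.3). SAP rule: 95.0% interval, one-sided 0.025 (SAP 10.2).

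**1. The protocol's boundary reproduces.** The O'Brien-Fleming-type spending function is α(t) = 2[1 − Φ(z₀.₉₈₇₅/√t)]. Cumulative spend is 0.000104, 0.006048 and 0.025. Solving with correlations √(nᵢ/nⱼ) gives z = 3.710, 2.511 and 1.993, that is nominal 0.0001, 0.0060 and 0.0231. These match Protocol 6.4.5 at its stated precision.

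**2. Overall one-sided error, final at 90 cases.** This is the probability under the null of crossing at any look (multivariate normal, interim levels as in the protocol).

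| Efficacy looks taken | Final at 0.023 | Final at 0.025 |
|---|---|---|
| 30 and 60 | 2.49% | 2.68% |
| 60 only | 2.48% | 2.67% |
| 30 only | 2.30% | 2.50% |
| none | 2.30% | 2.50% |

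The bottom row is the nominal level itself. With both looks and a final 0.025, the error is 2.58% if the final falls at 75 cases and 2.72% at 100.

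**3. Matching interval.** 1 − 2 × 0.023 = 0.954, so a test at 0.023 corresponds to a 95.4% interval (z = 1.995).

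**4. Decisions at exactly 90 cases.** In the exact conditional binomial with q = 4/9, P(X ≤ 30) = 0.0210 and P(X ≤ 31) = 0.0347, so the critical split is 30 v 60 at both levels. A Wald test gives the same answer, with Z = [log(d_v/d_p) − log 0.80] / √(1/d_v + 1/d_p):
- 30 v 60: Z = (−0.693 + 0.223)/0.2236 = −2.10, p = 0.018.
- 31 v 59: Z = (−0.644 + 0.223)/0.2218 = −1.90, p = 0.029.

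No split lies between the two levels.

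**5. Decisions at other totals.** Over totals 61 to 110, the Wald test puts one split between 0.023 and 0.025 at 68, 73, 81, 86, 91, 96, 101 and 106 cases. Example, 91 cases, 31 v 60: VE = 1 − 31/60 = 48.3%; standard error √(1/31 + 1/60) = 0.2212; Z = (−0.660 + 0.223)/0.2212 = −1.98; p = 0.0240. The lower VE limit is 1 − exp(−0.660 + z × 0.2212):
- z = 1.960 (95.0%): 20.3%, success under SAP 10.2.
- z = 1.995 (95.4%): 19.7%, failure at 0.023.

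**6. Final level when the count is not 90.** Holding the interim bounds and spending all remaining alpha gives 0.0242 at 75 cases, 0.0231 at 90 and 0.0226 at 100. Applying the spending function literally at t = 75/90 gives a cumulative 0.0141 and a nominal level of only 0.0123. After the 30-case look alone, the spend-all level is 0.02496; after the 60-case look alone, 0.0231.

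**The case against.** The best reply is that there is little to fix. Protocol 6.4.5 names 2.5% as the overall rate, so the 0.025 in 6.4.4 reads naturally as that overall level, and SAP 10.2 merely repeats it. The SAP describes itself as expanding on the protocol, so the 6.4.5 boundaries still apply without restatement. At the planned 90 cases the exact three-look binomial error is 2.19% under either level, and Protocol 6.3.2.3 regards that calculation as a close guide to the power of the Cox test. The final test may never be reached: both documents allow stopping for infeasibility, and SAP 10 allows the efficacy tables to be dropped if cases are few.

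The points about size and conditionality stand. The reading of 0.025 as only an overall level does not survive SAP 10.2, which makes it a 95.0% interval applied to the final data; that is a nominal final-look rule. Protocol 6.4.5 expressly gives the final analysis 0.023. The unchanged critical count depends on the total being exactly 90, which SAP 6.2 does not require. The protocol does hold the boundaries, so their absence from SAP 6.6 is secondary to the conflict in SAP 10.2.

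**Conclusion.** The contradiction holds. With the 60-case look taken and the final at 90 cases, the SAP rule raises overall one-sided error from about 2.5% to about 2.7%: an excess of 0.18 percentage points over 2.5% (2.68% with both looks). If no efficacy look is taken, or only the 30-case look, 0.025 with a 95.0% interval is valid and there is no real excess.

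The error figures are normal approximations and assume the interim looks use the protocol's levels. The split examples assume equal person-time and no strata, so they illustrate what the stratified Cox model could produce and do not predict it. The effect is small, but two thresholds for the primary claim should be reduced to one before unblinding.

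**What to change.** - **SAP 10.2:** replace the fixed 0.025 / 95.0% rule. Suggested wording: *The final analysis spends all alpha remaining from one-sided 0.025 after the efficacy looks actually taken, whatever the final case count. The nominal level is computed from the actual case counts: 0.023 with a 95.4% CI if looks are taken at 30 and 60 and the final is at 90; 0.025 with a 95.0% CI if no efficacy look is taken.* Other conventions are possible, but the text must choose one, because literal spending at a short count gives a much stricter level.
- **SAP 6.6:** add the efficacy looks with the Protocol 6.4.5 boundaries. In SAP 2.1, settle whether the looks are firm or optional.
- **SAP 10.2.1:** match the interval in the code, for example ALPHA=0.046 with RL on the MODEL statement for a 95.4% CI.
- **Protocol 6.4.4:** say that 0.025 is the overall one-sided level.
- **SAP 10 (related gap):** the primary analysis is repeated if cases arrive between data cut-off and lock. State whether the 90-case result or the repeat decides success.

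The cost is wording and one SAS option. Moving the final level from 0.025 to 0.023 with both looks lowers power at VE 61% from 0.868 to 0.860 or from 0.928 to 0.923, depending on the variance used (0.5 to 0.7 percentage points before rounding). In the conditional binomial at exactly 90 cases it costs nothing. This agrees with the statement in Protocol 6.3.2.3 that "such monitoring has a negligible impact on power".

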#### **10.2.1.** Sample SAS code for time to event analysis:

Notations

Timevar = the variable that gives the time to occurrence Censorvar = the variable indicating whether timevar is censored, where 1 = censored, 0 = not censored (event) Trtmnt = study product (placebo or ZIKVwt DNA) Stratavar = variable indicating baseline ZIKV serostatus

#### Cox Proportional Hazard

SAS Code for stratified Cox Regression [4] to obtain Vaccine Efficacy and 95% CI for Vaccine Efficacy:

```
Proc phreg;
CLASS trtmnt (ref = 'placebo') / param = ref;
STRATA stratavar;
MODEL timevar*censorvar(1)=trtmnt (and any covariates)/rl;
ODS OUTPUT ParameterEstimates=ests (keep=HazardRatio HRUpperCL
HRLowerCL);
RUN;
```

Calculate the following from the estimates obtained from the PROC PHREG output:

Vaccine Efficacy = 1 – HazardRatio Lower 95% CI= 1 – HRUpperCL Upper 95% CI= 1 – HRLowerCL

Similar code will be used to fit the cox regression combined across ZIKV serostatus stratum by removing the STRATA statement on PROC PHREG.

## 10.3. Analysis of Clinical Signs and Symptoms of ZIKV Illness

For confirmed ZIKV cases (primary endpoint), the number and percentage of subjects reporting each sign/symptom collected on the ZIKV Endpoint eCRF will be presented by study group in Table 51 through Table 53, Appendix 1. Continuous summary statistics for the duration of ZIKV illness, defined as date of resolution or death minus illness onset date plus 1 will be shown in Table 57 through Table 59, Appendix 1.

#### **11. REPORTING CONVENTIONS**

P-values  $\geq 0.001$  and  $\leq 0.999$  will be reported to 3 decimal places; p-values less than 0.001 will be reported as "<0.001"; p-values greater than 0.999 will be reported as "> 0.999". The mean, standard deviation, and any other statistics other than quantiles, will be reported to one decimal place greater than the original data. Quantiles, such as median, or minimum and maximum will use the same number of decimal places as the original data. Proportions will be presented as two decimal places; values <0.01 will be presented as "<0.01". Percentages, including VE, will be reported to the nearest tenth. Estimated parameters, not on the same scale as raw observations (e.g. regression coefficients) will be reported to 3 significant figures.

#### **12. TECHNICAL DETAILS**

SAS version 9.3 or above will be used to generate all tables, figures and listings.

#### 14. LISTING OF TABLES, FIGURES AND LISTINGS

Table, figure, and listing shells are presented in Appendices 1, 2, and 3, respectively.

Other	X	X.X
 Subjects may be counted under multiple criteria N = number of subjects screened		
Note, there was only a single segment of the protocol A and Part B	for screening subjects in	nto both Part

### Table 1: Summary of Screen Failures, All Enrolled Subjects

 Table 2:
 Summary of Screen Failures by Site, All Enrolled Subjects

Reason for Screen	(N	Site 1 = XX)	(	Site 2 N = XX)	[Repeat fo	or all sites]
Failure 	n	%	n	%	n	%
Not Eligible						
Laboratory finding(s)						
Physical exam finding(s)						
Medical history						
Other						
Eligible but not Randomized						
Time commitment						
Concern of potential risks						

Reason for Screen	(N	Site 1 ( = XX)	(N	Site 2 = XX)	[Repeat fo	or all sites]
Failure 	n	%	n	%	n	%
Number of procedures/blood draws						
Unable to contact subject						
Study closed out						
Other						
1.Subjects may be counted N = number of subjects sc	l under m reened	ultiple criteri	a			·
Note, there was only a sing Part B	gle segme	ent of the prof	tocol for s	screening sul	bjects into both	Part A and

Subject	Group ZIKVw inje (N	0 1: 4 mg 7t DNA, 2 ctions (=X)	Group ZIKVw injec (N=	2: 4 mg t DNA, 4 etions =X)	Group ZIKVwi injec (N=	3: 8 mg t DNA, 4 tions =X)	All Su (N=	ıbjects =X)
Disposition	n	%	n	%	n	%	n	%
Randomized								
Received First Administration								
Received Second Administration								
Received Third Administration								
Early Termination								
Completed Per Protocol Population 								
Completed mITT Population 								
$^{1}$ Subjects removed from the per protocol population and mIT N = number of subjects randomized	T are listed	l in Listing 8						

### Table 3:Subject Disposition by Study Group- Part A

Table with similar format:

### Table 4:Subject Disposition by Study Group- Part B

Subject	Si (N =	te 1 = XX)	Sit (N =	e 2 XX)	All Su (N=	ıbjects =X)
Disposition	n	%	n	%	n	%
Screened	х	x.x	х	x.x	х	X.X
Randomized						
Received First Administration						
Received Second Administration						
Received Third Administration						
Early Termination						
Lost to Per Protocol Before Administration 3						

